8.1.1 Return and Retention of Study Drug

Destruction and Return

At the end of the study, unused supplies of regorafenib should be destroyed according to institutional policies. Destruction will be documented in the Drug Accountability Record Form. The certificate of destruction should be sent to Bayer.

A completed “Unused Study Drug Disposition Form Destruction or Return Confirmation” should be sent to Bayer at the following address:

E-mail: [contact]

OR

[contact]

OR

Mail: (VP of Medical Affairs named in contract) at

Bayer HealthCare Pharmaceuticals
[name]
[name]

Accountability

All study drugs will be stored at the investigational site in accordance with Good Clinical Practice (GCP) and Good Manufacturing Practices (GMP) requirements and the instructions given by the clinical supplies department of the Institution and will be inaccessible to unauthorized personnel.

The study pharmacist at each participating site will be responsible for maintaining a record of shipment, receipt and dispensation of study medication(s). The study pharmacist will utilize an NCI drug accountability template for documenting dates, and amounts/doses received from the sponsor and dates, patient initials and doses dispensed to the patient.

8.1.2 Treatment compliance

The study Research Coordinator(s) and Data Manager(s) will be responsible for drug accountability of dispensed and returned drug in accordance with the CISO SOP 8.0. The CISO standard pill diary in English and Spanish will be used.

9.0 CORRELATIVES/SPECIAL STUDIES

All correlative studies are mandatory. The samples will be collected for correlative studies which will be determined by current scientific knowledge available at the end of the study. For sites not at USC, store all samples for batch shipping.

9.1 Archival Tissue

Slides require 10 slides of unstained tumor 10 um thick from paraffin embedded tumor blocks or fresh frozen tissue. In lieu of slides, a tumor block may be sent. If possible, the tumor block should be large enough to provide the slides described above.

9.2 Plasma Collection

The blood will be collected prior to initiation and at time of progression/off study. The blood collection will require 2 tubes of blood (two purple top tubes).

[name] laboratory will receive and process information. [name] Laboratory
USC Norris Cancer Center
[name]
[name]
[contact]

10.0 STATISTICAL CONSIDERATIONS

10.1 Study Design/Study Endpoints

The 6-month PFS rate will be the primary endpoint (see definition at section 6.1.10). Two parallel Simon's 2-stage phase II trials will be conducted to evaluate the efficacy of regorafenib in patients with advanced carcinoid (cohort A) or pancreatic islet cell tumors (cohort B).¹⁴ Two randomized phase III trials [refs 10-11] that were completed for advanced pancreatic islet cell tumors observed the median PFS was about 11 months and 6-month PFS rate was 71% in arm of the anti-VEGF therapy. Two small phase II trials of anti-VEGF agents that were conducted among patients with advanced carcinoid tumor [refs 14-15] showed that the median PFS was about 6 months and 6-month PFS rate was 45%. Therefore 6-month PFS rate of 65% for patients with advanced carcinoid and 80% for patients with advanced pancreatic islet cell tumors would be promising for further investigation. Otherwise observation of 40% and 60% 6-month PFS rate would be considered ineffective in the setting of advanced carcinoid and pancreatic islet cell tumors, respectively.

For cohort A, a 6-month PFS rate of 40% (under the null hypothesis) would be considered as disappointing and 65% or higher (under the alternative hypothesis) would be encouraging. For cohort B, a 57% rate (under the null hypothesis) would be considered as not interesting, and 80% or higher (under the alternative hypothesis) would be promising. The 6-month PFS rates under the null and alternative hypotheses were chosen based on a phase II consortium trial in the similar settings (NCI Protocol #: 8233). We need a total of 24 patients with carcinoid tumors (cohort A) and 24 patients with pancreatic islet cell tumors (cohort B).

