
Statistical Methodology
	
The 6-month PFS rate will be the primary endpoint. Two parallel Simon's 2-stage phase II trials will be conducted to evaluate the efficacy of regorafenib in patients with advanced carcinoid (cohort A) or pancreatic islet cell tumors (cohort B). For cohort A, a 6-month PFS rate of 40% would be considered as disappointing and 65% or higher would be encouraging. For cohort B, a 57% rate would be considered as not interesting, and 80% or higher would be promising. We need a total of 24 patients with carcinoid tumors (cohort A) and 24 patients with pancreatic islet cell tumors (cohort B).
 
The study design of both trials has 80% power to demonstrate the efficacy of regorafenib. The type I error rate is 5.1% and 5.3%, for cohort A and B, respectively. We designed the trials with type I error rate a little higher than 5% because the tumors are rare and the sample size should be as small as possible.

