10.2 Sample Size and Accrual

In cohort A, 11 patients will be enrolled in stage I. If 5 or more patients remain alive and progression-free at 6 months, we will continue to enroll until a total of 24 patients are enrolled. If 4 or fewer patients out of the first 11 patients remain alive and progression-free at 6 months, we will suspend the accrual. If we observe **14** or more patients are alive and progression-free at 6 months, regorafenib would be considered promising for cohort A as long as it is tolerable.

In cohort B, 11 patients will be enrolled in stage I. If 7 or more patients remain alive and progression-free at 6 months, we will continue to enroll until a total of 24 patients are enrolled. If 6 or fewer patients out of the first 11 patients remain alive and progression-free at 6 months, we will suspend the accrual. If we observe **18** or more patients are alive and progression-free at 6 months, regorafenib would be considered promising for cohort B as long as it is tolerable.

We will not suspend accrual when the number of patients enrolled meets the goal for the number of patients required for stage I in each trial but the decision of suspending the accrual during stage I cannot be reached due to the insufficient follow-up.

The study design of both trials has 80% power to demonstrate the efficacy of regorafenib. The type I error rate is 5.1% and 5.3%, for cohort A and B, respectively. We designed the trials with type I error rate a little higher than 5% because the tumors are rare and the sample size should be as small as possible. The sample size calculation was based on a single-arm 2-stage Simon's Minimax phase II Design. An online program (Clinical Trial Design Systems) developed by Duke Cancer Institute was used to perform the calculation (<http://www.dukecancerinstitute.org/research/shared-resources/biostatistics/clinical-trial->

[design-systems/](#)).

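### Does the 60% benchmark in the section 10.1 rationale undermine cohort B's 57% null and its stated 5.3% type I error?

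*Combined protocol and SAP*

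**What the plan says.** Section 10.1 gives unfavourable 6-month PFS rates in two consecutive paragraphs.

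- The rationale paragraph, after reviewing earlier trials and naming 65% (carcinoid) and 80% (islet cell) as promising, adds: "Otherwise observation of 40% and 60% 6-month PFS rate would be considered ineffective in the setting of advanced carcinoid and pancreatic islet cell tumors". The 60% belongs to cohort B.
- The hypothesis paragraph says: "For cohort B, a 57% rate (under the null hypothesis) would be considered as not interesting", with the alternative worded as "80% or higher (under the alternative hypothesis) would be promising". It adds that the null and alternative rates "were chosen based on a phase II consortium trial in the similar settings (NCI Protocol #: 8233").

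The Study Summary (Statistical Methodology) agrees with the second paragraph: "For cohort B, a 57% rate would be considered as not interesting, and 80% or higher would be promising".

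Section 10.2 gives the rule. "In cohort B, 11 patients will be enrolled in stage I"; accrual continues if 7 or more are alive and progression-free at 6 months, and the drug is promising if 18 or more of 24 are. On error rates it says: "The type I error rate is 5.1% and 5.3%, for cohort A and B, respectively", and explains: "We designed the trials with type I error rate a little higher than 5% because the tumors are rare". Stated power is 80%.

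**The concern.** The rationale paragraph names four benchmark rates. Three of them (40%, 65% and 80%) equal the formal hypotheses exactly. Only cohort B's unfavourable rate differs, and it is paired with 40%, which is cohort A's formal null. A reader will therefore naturally take 60% as a second, conflicting null for cohort B.

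Section 10.2 states the type I error rates without repeating the true rates to which they apply. Someone who takes 60% from 10.1 and 5.3% from 10.2 would believe that a drug with a true 6-month PFS rate of 60% has a 5.3% chance of being called promising. The actual chance is higher, and it would no longer fit the plan's description of an error rate slightly above 5%. If 60% were really the intended null, 24 patients could not deliver both about 5% error and 80% power.

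**Working it through.** **Inputs (section 10.2, cohort B):** stage I n = 11, continue at 7 or more; stage II adds 13, total 24; success at 18 or more. Null 57% and alternative 80% from the hypothesis paragraph of 10.1; 60% from the rationale paragraph.

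**Formula.** With X1 ~ Bin(11, p) and X2 ~ Bin(13, p) independent,

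P(promising) = Σ over x = 7 to 11 of P(X1 = x) × P(X2 ≥ 18 − x).

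**Step 1: reproduce the plan's figure at p = 0.57.**

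| x | P(X1 = x) | P(X2 ≥ 18 − x) | Product |
|---|---|---|---|
| 7 | 0.22055 | 0.03701 | 0.00816 |
| 8 | 0.14618 | 0.11933 | 0.01744 |
| 9 | 0.06459 | 0.27459 | 0.01774 |
| 10 | 0.01712 | 0.48541 | 0.00831 |
| 11 | 0.00206 | 0.69747 | 0.00144 |
| Sum | | | 0.0531 |

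This is the stated 5.3%. At p = 0.80 the same sum is 0.8015, the stated 80% power. The cohort A rule (5 or more of 11, 14 or more of 24) gives 0.0514 at 40% and 0.8049 at 65%, again as stated.

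**Step 2: the same rule at p = 0.60.** The five products are 0.01369, 0.02990, 0.03131, 0.01528 and 0.00280, and their sum is 0.0930. The ratio to step 1 is 0.0930 / 0.0531 = 1.75.

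**Step 3: early stopping.** P(X1 ≤ 6) is 0.5495 at 57% and 0.4672 at 60%. Expected sample size is 11 + 13 × (1 − 0.5495) = 16.9 and 11 + 13 × (1 − 0.4672) = 17.9.

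**Step 4: which rate was the design built on?** A minimax search for 57% vs 80%, with alpha up to 5.35% and power of at least 80%, returns exactly 7 of 11 then 18 of 24. That agrees with 57% but does not prove it, because the 5.35% ceiling is taken from the stated 5.3%. With alpha allowed up to 10%, the search for 60% vs 80% returns the same boundaries (alpha 9.3%, power 80.1%). So the cut-offs alone do not identify the null. The stated 5.3% does, since the rule gives 5.3% at 57% and 9.3% at 60%, and so does the explicit null label.

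**Step 5: does the choice of benchmark change what a minimal success shows?** Section 10.3 plans a 95% Wilson interval. For 18/24, read as two-sided (z = 1.96) and ignoring the two stages:

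- centre = (0.75 + 1.96²/48) / (1 + 1.96²/24) = 0.7155
- half-width = 0.1645
- interval = 55.1% to 88.0%

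The lower limit is below both 57% and 60%, so the planned interval does not separate the two benchmarks. A one-sided 95% Wilson bound (58.5%) would fall between them, but the plan does not specify that bound.

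**Step 6: where each rate is used.**

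| Element | Uses 57% | Uses 60% |
|---|---|---|
| Labelled null, 10.1 | yes | no |
| Study Summary | yes | no |
| Stated 5.3% error, 10.2 | yes | no |
| Cut-offs and n, 10.2 | fixed counts, error quoted at 57% | no |
| Analyses, 10.3 | neither | neither |
| Rationale sentence, 10.1 | no | yes |

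**The case for a change.** The strongest case for acting is that a benchmark for the primary endpoint is stated two ways in one section and that the gap is material: 9.3% is not slightly above 5%. If 60% were the intended null, a 12-then-32 design (8 or more, then 24 or more; alpha 5.32%, power 80.0%) would be needed to keep roughly the stated operating characteristics. Only the sponsor can say for certain which rate was meant, and the correction costs one number.

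The discrepancy and the arithmetic stand. The step from there to a flaw in the plan does not. Type I error is defined at the null, and the plan labels its null as 57% in the paragraph directly after the stray figure. A plan is not obliged to report the rejection probability at some other rate. To be misled, a reader would have to attach 5.3% to 60% while passing over that label, its cited source and the Study Summary.

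The sentence can also be read literally as being about an observed rate. An observed 60% is about 14 of 24 (0.60 × 24 = 14.4), which fails the 18 of 24 rule, so nothing conflicts on that reading. I give this little weight: the pairing with 40% makes the null reading more natural, and 60% is not the decision cut-off either, since 17/24 (70.8%) also fails.

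**Conclusion.** The concern is correct as an observation but calls for no change to the plan. The 60% is a clerical slip in a background sentence. Followed as written, the trial enrols the same patients, applies the same stage I and final rules, and reports an error rate (5.3%) and power (80%) that are correct for its declared hypotheses of 57% vs 80%. Substituting 57% in the rationale would leave all of that unchanged, and an analyst would use 57% without hesitation.

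The slip could matter only if 60% were the true intended null. The cohort B error would then be 9.3%, not 5.3%. Nothing operative in the document points that way: the label, the source, the Study Summary and the reported error rate all give or match 57%. The conclusion rests on that reading and on exact binomial calculation with the section 10.2 rule applied as stated.

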10.2 Sample Size and Accrual

In cohort A, 11 patients will be enrolled in stage I. If 5 or more patients remain alive and progression-free at 6 months, we will continue to enroll until a total of 24 patients are enrolled. If 4 or fewer patients out of the first 11 patients remain alive and progression-free at 6 months, we will suspend the accrual. If we observe **14** or more patients are alive and progression-free at 6 months, regorafenib would be considered promising for cohort A as long as it is tolerable.

In cohort B, 11 patients will be enrolled in stage I. If 7 or more patients remain alive and progression-free at 6 months, we will continue to enroll until a total of 24 patients are enrolled. If 6 or fewer patients out of the first 11 patients remain alive and progression-free at 6 months, we will suspend the accrual. If we observe **18** or more patients are alive and progression-free at 6 months, regorafenib would be considered promising for cohort B as long as it is tolerable.

We will not suspend accrual when the number of patients enrolled meets the goal for the number of patients required for stage I in each trial but the decision of suspending the accrual during stage I cannot be reached due to the insufficient follow-up.

The study design of both trials has 80% power to demonstrate the efficacy of regorafenib. The type I error rate is 5.1% and 5.3%, for cohort A and B, respectively. We designed the trials with type I error rate a little higher than 5% because the tumors are rare and the sample size should be as small as possible. The sample size calculation was based on a single-arm 2-stage Simon's Minimax phase II Design. An online program (Clinical Trial Design Systems) developed by Duke Cancer Institute was used to perform the calculation (<http://www.dukecancerinstitute.org/research/shared-resources/biostatistics/clinical-trial->

[design-systems/](#)).

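### After stage I, section 10.2 enrols to 24 even when a cohort can no longer reach its cut-off; a curtailment sentence would be a cheap improvement, not the correction of an error

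*Combined protocol and SAP*

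**What the plan says.** Section 10.2 names the design: "The sample size calculation was based on a single-arm 2-stage Simon's Minimax phase II Design". The hypotheses are in section 10.1: "For cohort A, a 6-month PFS rate of 40% (under the null hypothesis) would be considered as disappointing and 65% or higher" is the alternative, and "For cohort B, a 57% rate (under the null hypothesis) would be considered as not interesting, and 80% or higher" likewise.

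The stage I rules in section 10.2 are, for cohort A, "If 4 or fewer patients out of the first 11 patients remain alive and progression-free at 6 months, we will suspend the accrual", and for cohort B, "If 6 or fewer patients out of the first 11 patients remain alive and progression-free at 6 months, we will suspend the accrual". A cohort that passes goes on to full size: "we will continue to enroll until a total of 24 patients are enrolled". The final rule for cohort A is: "If we observe 14 or more patients are alive and progression-free at 6 months, regorafenib would be considered promising for cohort A". Cohort B needs 18 or more of 24.

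Four other statements bear on the point.

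- Section 10.2 does not pause accrual at 11 patients while follow-up is too short for the stage I decision to be reached.
- Sections 6.1.10 and 10.3 count progression or death within 182 days as a 'no'. Withdrawal, loss to follow-up and unknown status also count as 'no', and section 10.3 adds the start of another therapy. Only patients who never start regorafenib are replaced.
- Section 10.2 explains a type I error slightly above 5% by saying that the tumors are rare and "the sample size should be as small as possible".
- Section 11.6.3 gives the data and safety monitoring committee a general remit for interim efficacy and futility analyses on institutional trials. It states no criterion for this one.

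**The concern.** A success cannot be counted until Day 182, but a failure is final as soon as it is established. Scans begin in week 3 of cycle 2 and recur every two cycles (sections 5.2.5 and 10.3), so many failures are known well before six months. The cohort's go/no-go result can thus be settled while places remain open, and the text then still fills them.

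At stake are patients with rare tumors who would enter a cohort that can no longer be declared promising. Section 1.1 describes approved drugs: sunitinib and everolimus for pancreatic tumors, and everolimus for progressive non-functional tumors of gastrointestinal or lung origin.

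**Working it through.** **1. The plan's own figures.** Let r1 be the largest stage I count that stops the cohort and r the largest final count that is not a success. From section 10.2, A has r1 = 4 of 11 and r = 13 of 24; B has r1 = 6 of 11 and r = 17 of 24. The probability of success at true rate p is

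Σ over x from r1+1 to 11 of P(X = x) × P(Y ≥ r + 1 − x), with X ~ Bin(11, p) and Y ~ Bin(13, p).

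| Cohort | Null / alternative | Type I error | Power | Stage I stop under null |
|---|---|---|---|---|
| A | 0.40 / 0.65 | 0.0514 | 0.8049 | 0.533 |
| B | 0.57 / 0.80 | 0.0531 | 0.8015 | 0.550 |

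These agree with the stated 5.1%, 5.3% and 80%.

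**2. When failure becomes certain.**

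- Cohort A, overall: 24 − 14 = 10 'no' results are affordable, so the 11th settles it. Stage I: 11 − 5 = 6 are affordable, so the 7th settles it.
- Cohort B, overall: 24 − 18 = 6 are affordable, so the 7th settles it. Stage I: 11 − 7 = 4 are affordable, so the 5th settles it.

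A cohort A that just passes stage I (5 of 11) already has 6 'no' results, and 5 more among the next 13 patients end its chances. A cohort B that just passes (7 of 11) has 4, and 3 more end its chances.

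**3. Effect of stopping there on error rates.** A cohort A with 11 'no' results can reach at most 24 − 11 = 13 successes, and a cohort B with 7 at most 24 − 7 = 17. Both are below the cut-off. No stopped cohort could have been a success, so type I error and power are exactly those in step 1.

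**4. How often it happens, with immediate outcomes (exact).** This is an upper bound, because it ignores the delay before a failure is known. At least one of the 24 places remains when failure is certain in 39.0% (A) and 37.9% (B) of null cohorts. Given a stage I pass, the mean number of places left is 3.6 (A) and 4.7 (B).

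**5. With delayed outcomes (20,000 simulated cohorts per scenario).** The Study Summary estimates one patient per month and four years for both cohorts: 48 patients / 48 months = 1 per month, or 0.5 per cohort if split evenly. The following are assumptions, not in the documents: Poisson accrual; exponential PFS with daily hazard −ln(p)/182; and two timings of knowledge. In the first, a failure is known at the next scan (Day 28 + 21 = 49, then 105 and 161) or at Day 182. In the second, it is known only at Day 182.

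| Null cohort, failures known | Pass stage I | Patient enters after certain failure, given pass | Same, all null cohorts | Mean such patients, given pass | Mean, all null cohorts |
|---|---|---|---|---|---|
| A, at scans | 0.471 | 0.674 | 0.471 × 0.674 = 0.32 | 2.31 | 0.471 × 2.31 = 1.09 |
| A, at 6 months | 0.466 | 0.523 | 0.466 × 0.523 = 0.24 | 1.53 | 0.466 × 1.53 = 0.71 |
| B, at scans | 0.451 | 0.728 | 0.451 × 0.728 = 0.33 | 3.29 | 0.451 × 3.29 = 1.48 |
| B, at 6 months | 0.451 | 0.620 | 0.451 × 0.620 = 0.28 | 2.45 | 0.451 × 2.45 = 1.10 |

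Under the alternatives, the share of all cohorts is 4–6% (A) and 6–8% (B). If a single cohort accrued one patient per month, the null shares would fall to 10–22% (A) and 16–25% (B), because more patients enter before failures are known.

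**6. Stage I and stage II separated (scan-time detection).** If stage I waits for all 11 outcomes, expected null enrolment is about 18.4 (A) and 18.3 (B). If stage I stops at the deciding 'no', it is about 17.4 and 16.7. With stage II curtailment as well, it is about 16.3 and 15.2. Stage II alone therefore saves 17.4 − 16.3 = 1.1 (A) and 16.7 − 15.2 = 1.5 (B). Both together save 18.4 − 16.3 = 2.1 (A) and 18.3 − 15.2 = 3.1 (B). If failures are known only at six months, the combined savings are about 1.5 (A) and 2.3 (B).

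**The case against.** One futility look followed by enrolment to the full size is how a Simon two-stage design works, and curtailment is an optional refinement. A reader might infer from the missing rule that the design is faulty or its error rates misstated. The documents do not support that: the figures reproduce.

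A reader might also take the remark about the smallest sample as a promise to minimise expected enrolment. In context it explains a type I error slightly above 5% at a planned 24, and a Minimax design minimises the maximum size. Curtailment is in keeping with the remark but is not required by it.

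A third tempting inference is that the whole saving of 2 to 3 patients comes from a missing rule. Section 10.2 lets accrual run only while the stage I decision cannot be reached. At the 7th (A) or 5th (B) 'no' it can be, so an early stage I stop is arguably already allowed. Only the stage II part is clearly absent.

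Three further objections stand in part.

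- The monitoring committee could close a cohort under its general remit. Without a criterion, though, nothing in these documents would trigger closure.
- A 'no' needs defining. Under note 10 of the Study Calendar, patients who leave treatment without progression are still scanned until progression, so being off drug is not a final 'no'. Section 10.3 analyses all who start regorafenib, whereas section 10.4 limits the primary analysis to eligible patients. A patient later found ineligible could leave the tally.
- Stopping on a count of failures biases the observed 6-month PFS proportion downward, and the Wilson interval in section 10.3 treats the sample size as fixed. Late patients would also have added to the PFS, response, OS and toxicity estimates. Against this, response and OS are to be analyzed descriptively, and section 10.5 measures biomarkers only if regorafenib is recommended for further study.

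**Conclusion.** The point holds as a low-cost improvement to a valid design. Once a cohort passes stage I, section 10.2 fills it to 24 even if 11 (A) or 7 (B) final 'no' results have already put success out of reach. At the planned accrual, patients would enter after that point in about 24–32% (A) and 28–33% (B) of null cohorts, and in about 4–8% of cohorts if the drug works.

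The undisputed stage II saving is about 0.7–1.1 (A) and 1.1–1.5 (B) patients per null cohort. It becomes 1.5–2.1 (A) and 2.3–3.1 (B) only if stage I is now read as waiting for all 11 outcomes. The limits of 11 and 7, and the unchanged error rates, are exact provided the running tally and the final decision use the same patients. The frequencies and savings rest on exponential PFS, Poisson accrual at 0.5 per month per cohort, and the two assumed detection timings.

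**What to change.** Add to section 10.2:

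> Accrual to a cohort closes as soon as its cut-off can no longer be reached: cohort A at the 7th 'no' among the first 11 patients or the 11th overall; cohort B at the 5th 'no' among the first 11 or the 7th overall. A 'no' counts only for a patient in the primary data analysis set and only when irreversible under 6.1.10 and 10.3 (progression or death within 182 days, withdrawal, loss to follow-up, or start of another therapy). Being off study drug alone does not count. Patients already enrolled continue per protocol.

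Reconcile the primary analysis set between sections 10.3 and 10.4, so that the tally and the final decision rest on the same patients.

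The rule needs a running count of final 'no' results. Sample sizes, cut-offs, type I error and power stay as stated. A cohort closed early will have slightly less precise toxicity, response and OS estimates. The reported 6-month PFS rate will be biased downward by about 1–2 percentage points on average under the null, so the report should state that the cohort closed early.

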5.4 Study Calendar

Cycles will be 28 Days. Regorafenib will be taken orally Days 1-21 of each Cycle. For first cycle all labs and EKG should be done within 7 days of first receiving study drug. For the first cycle, Imaging studies should be done within 28 days of first receiving study drug.

Parameter	Pre-Treatment ⁶	Day 1 of All Cycles ¹ ²	Day 8, Day 15 And 22 of Cycle 1 and 2 only ¹²	Day 15 of all Cycles ¹ ²	One Day of Week 3 Of every other Cycle (starting with Cycle 2)	Off study	Follow-up
Informed Consent	X						
Pill Diary		X				X	
History & Physical Exam	X	X					
Weight, SWOG Performance Status, Con Meds	X	X				X	
Adverse Event/Toxicity Evaluation	X	X					
WBC (differential), Hgb, Platelets	X	X		X			
Complete Metabolic Panel, Phosphorus, Magnesium, LDH	X	X	Liver function	X			
Lipase	X	X					
Thyroid Function (TSH, T3, T4)	X	X ³					
PT/PT-INR, PTT	X	X ^{3,9}					
Urinalysis for proteinuria	X	X					
5HIAA	X	X					
Serum Chromogranin	X				X		
Octreotide scan	X				Cycle 2 only		
EKG	X	X ³					
CXR (if CT of chest not done)	X ⁷				X ⁷		
BP Monitoring		X	X				
Radiology, x-ray or Scans for disease measurement ²	X ⁸				X		X ¹⁰
Archival tumor tissue	X ⁸						
Plasma	X ⁸					X ⁸	
Urine Pregnancy Test	X ⁵	X ⁵					
Survival Follow-up							X ¹¹

- 1 If used to follow measurable disease.
- 2 Within 28 days of Cycle 1, Day 1.
- 3 As clinically indicated.
- 4 Paraffin embedded tissue must be available for review.
- 5 For women of childbearing potential
- 6 Confirm response within 4 weeks.
- 7 Not required if CT scan of the chest is done.
- 8 See section 9. For plasma two purple top tubes to the [name] lab.
- 9 Close monitoring (day 5 of cycle 1 and day 1 of each cycle) of PT/PT-INR and PTT is mandatory for patients on agents such as warfarin and heparin.
- 10 Patients that come off for reasons other than disease progression will have their standard of care scans measured via RECIST until progressive disease, to determine date of disease progression
- 11 Patients will be followed up via phone call, medical records or database search until death to determine survival time
- 12 All study visits allow a +/- 7 day window

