6.1.9 Overall Survival (OS)

Overall survival is defined as from start of treatment until death due to any cause. Otherwise OS is censored on the last day patients are known to be alive.

6.1.10 The primary endpoint:

The 6-month PFS rate is the primary endpoint. The 6-month PFS is dichotomous, *yes* or *no*. Radiographic scan for disease measurement that is done within ± 14 days of the 6-month landmark (Day 182 since first receiving study drug) will be counted to determine the 6-month PFS status. Patients who are alive and progression-free at 6 months (182 days) since first starting regorafenib will be counted as 'yes' for the 6-month PFS. Patients who progress or die within 6 months of starting regorafenib will be counted as 'no' for the 6-month PFS. Patients whose status of progression or death at 6 months is unknown due to early withdrawal, loss-of-follow-up, or other reasons will be also counted as 'no' for 6-month PFS.

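### The 80% power is correctly computed, but 10.2 states no allowance for unknown Day-182 status, which is scored 'no', and no scan after early stopping is tied to Day 182

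*Combined protocol and SAP*

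**What the plan says.** **Design.** Section 10.1 sets the rates. The first cohort (A, carcinoid) has this pair: "a 6-month PFS rate of 40% (under the null hypothesis) would be considered as disappointing and 65% or higher (under the alternative hypothesis"). The second (B, pancreatic islet cell) has this one: "a 57% rate (under the null hypothesis) would be considered as not interesting, and 80% or higher (under the alternative hypothesis) would be promising". Section 10.2 gives the rules. In cohort A, "If 4 or fewer patients out of the first 11 patients remain alive and progression-free at 6 months, we will suspend the accrual", and for the final decision, "If we observe 14 or more patients are alive and progression-free at 6 months", the drug is called promising if tolerable. Cohort B continues at 7 or more of 11 and is promising at 18 or more of 24. Section 10.2 then states: "The study design of both trials has 80% power to demonstrate the efficacy of regorafenib".

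**Scoring.** Section 6.1.10 defines the endpoint as yes or no at Day 182. On missing status it says: "Patients whose status of progression or death at 6 months is unknown due to early withdrawal, loss-of-follow-up, or other reasons will be also counted". The score these patients receive is 'no'. Section 10.3 does the same for patients who withdraw, are lost, or start another therapy before their status is determined, and keeps them in the denominator. Only patients who never start regorafenib are replaced.

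**Imaging after stopping.** The Off Study list (5.2.6) contains no tumor assessment. Follow-up after treatment is by phone every 3 months (4.6, 5.3). Footnote 10 of the Study Calendar (5.4) adds: "Patients that come off for reasons other than disease progression will have their standard of care scans measured via RECIST until progressive disease". It sets no interval and does not mention Day 182.

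**The concern.** Section 10.1 supports its target rates with published 6-month PFS figures; for pancreatic islet cell tumors the cited trials "observed the median PFS was about 11 months and 6-month PFS rate was 71"%. The trial itself counts patients documented as progression-free at Day 182, with every unknown treated as a failure. If the targets were meant as true PFS rates, the observed 'yes' rate will sit below them by whatever share cannot be classified.

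The plan expects some unknowns: 10.3 provides a reporting category for status unknown because of early withdrawal, toxicities or other reasons. It does not ensure a usable scan near the landmark for a patient who stops early without progression.

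At stake is a false negative. An active drug that some patients stop for toxicity could miss 14 of 24 or 18 of 24 partly for want of a scan. The margin is thin: at the target rates the expected number of 'yes' patients is 24 × 0.65 = 15.6 against 14 needed, and 24 × 0.80 = 19.2 against 18 needed.

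**Working it through.** **Inputs.** From 10.1 and 10.2: stage I n = 11, stage II n = 13, total 24. Continue at r1 = 5 (A) or 7 (B); promising at r = 14 (A) or 18 (B). Null rates are 0.40 and 0.57; alternatives are 0.65 and 0.80.

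**Formula.** With X the stage I count,

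P(promising | p) = Σ from x = r1 to 11 of C(11,x) p^x (1−p)^(11−x) × P[Bin(13, p) ≥ r − x].

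**Step 1: the plan's own figures.** Terms at the alternative, from x = r1 upward:

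- A, p = 0.65: 0.0493 + 0.1310 + 0.2113 + 0.2150 + 0.1378 + 0.0517 + 0.0087 = 0.805.
- B, p = 0.80: 0.0555 + 0.1655 + 0.2660 + 0.2291 + 0.0853 = 0.801.

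At the null rates the same sum gives 5.14% (A) and 5.31% (B), against the stated 5.1% and 5.3%. All the stated figures reproduce, and power is essentially at 80%, with no reserve.

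**Step 2: an illustration of unknowns.** Let u be the share of truly progression-free patients who cannot be classified, independent of outcome. The 'yes' rate becomes p(1 − u); for example, 0.65 × 0.95 = 0.6175 and 0.80 × 0.95 = 0.76. The documents give no value of u, so every row after the first is an assumption.

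| u | A 'yes' rate | A power | B 'yes' rate | B power | Type I, A | Type I, B |
|---|---|---|---|---|---|---|
| 0 | 65.0% | 80.5% | 80.0% | 80.1% | 5.1% | 5.3% |
| 1% | 64.35% | 78.6% | 79.2% | 77.2% | 4.7% | 4.7% |
| 2% | 63.7% | 76.6% | 78.4% | 74.1% | 4.3% | 4.2% |
| 5% | 61.75% | 70.1% | 76.0% | 64.1% | 3.3% | 2.9% |
| 10% | 58.5% | 58.0% | 72.0% | 46.4% | 2.0% | 1.5% |

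In patients, u = 5% is an expected loss of 15.6 × 0.05 = 0.78 'yes' results in A and 19.2 × 0.05 = 0.96 in B.

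**Step 3: a less favourable model.** If u is instead a share of all patients and every unknown would have been 'yes', the rate is p − u. Power is then 63.7% (A) and 59.7% (B) at u = 5%, and 44.2% and 38.0% at u = 10%.

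**Step 4: which patients are exposed.** On treatment, scans fall in week 3 of every second cycle from cycle 2: days 155–161 (cycle 6) and 211–217 (cycle 8). As scheduled, neither lies in the Day 168–196 window, but a progression-free scan after Day 182 still settles the status as 'yes'. The exposure is therefore mainly patients who stop before Day 182 without progression and have no later usable scan.

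**Step 5: what a timed scan can recover.** It cannot help patients who withdraw, are lost or start another therapy before their status is determined. If, for illustration, half of u = 5% were recoverable, u would fall to 2.5%. The rates would be 0.65 × 0.975 = 0.634 and 0.80 × 0.975 = 0.78, and power 75.6% (A) and 72.5% (B).

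**The case against.** The strongest reply is that nothing in 10.2 is wrong. Section 10.1 refers to 6.1.10 for the endpoint, and 6.1.10 scores unknowns as 'no'. On that reading 65% and 80% are rates after unknowns are counted as failures, and the 80% stands as printed. The published figures do not settle the matter, because 10.1 also says that the null and alternative rates came from a phase II consortium trial in similar settings. How that trial, or the others cited, handled unknown status is not in the documents. This stands: a reader might infer that the 80% is a miscalculation, or holds only if every patient's status is known, and the text supports neither. What remains is that the plan does not say which rate is meant.

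Second, u is not in the documents, and it could be 1%, where the loss is about 2 points in A and 3 in B. This also stands; the table shows sensitivity and does not predict.

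Third, untimed does not mean unscanned. Footnote 10 scans are read by RECIST until progression, and 10.3 uses the ± 14-day window only when no other scan settles the status. Some early stoppers will be classified correctly as things are. That narrows the gap but does not close it, since nothing ensures a scan at or after Day 182.

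Fourth, scoring unknowns as 'no' is a deliberate, conservative choice. It lowers type I error, unknowns are reported as their own category, and a Kaplan-Meier estimate of 6-month PFS is also planned. This is a good reason to keep the rule. It does not restore the decision, which rests on the count.

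**Conclusion.** The power statement is arithmetically correct, at 80.5% (A) and 80.1% (B), but no allowance for unknown Day-182 status is stated. The follow-up schedule also leaves some of those unknowns to chance. If 65% and 80% are true PFS rates and unknowns are independent of outcome, power is 77%/74% (A/B) at an assumed u of 2%, 70%/64% at 5% and 58%/46% at 10%. If the targets already include unknowns as failures, the 80% stands and only the avoidable misclassification remains.

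It is tempting to attribute the whole loss to the missing timed scan. The documents do not support that: withdrawals, losses and therapy switches before status is determined stay 'no' whatever imaging is scheduled, and standard-of-care scans will resolve some of the rest. This is an inexpensive improvement to endpoint ascertainment and a clarification of the power statement. It does not call for a new sample size, new decision rules or a different scoring rule.

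**What to change.** 1. In footnote 10 of 5.4 and in 5.2.6, add: for a patient who stops regorafenib before Day 182 without progression and remains in follow-up, one of the standard-of-care scans is timed to Day 182 ± 14 days and read by RECIST.
2. In 10.2, add: the 80% power applies to the rate of the endpoint as defined in 6.1.10, with unknown status counted as 'no'; no separate allowance for unknown status has been made. Power at a few assumed values of u may be given alongside, but this is optional.

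**Cost.** One routine scan is scheduled, not added, for the few patients who stop early without progression, and the power statement becomes slightly less favourable.
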